# Aims

To compare the effectiveness of 7.0 mm-wide diameter implants with 5.0 mmconventional diameter implants placed immediately after tooth extraction in the molar region.

Test hypothesis: there is no difference in clinical outcomes between the two procedures, against the alternative hypothesis of a difference.

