# Study Design

Multicenter randomized controlled trial (RCT) of parallel group design. Each patient will provide only one implant-supported crown. For patients with multiple teeth to be extracted, the operator will be free, at the screening visit, to select the tooth to be included in the trial. The trial will have a duration of 5 years post-loading.

- Randomisation: using computer generated random numbers, centralized with sequentially sealed opaque envelopes provided by the study adviser.
- Allocation concealment: operators will know about the intervention to be delivered by opening a sealed envelope after the tooth has been extracted.
- Blinding: independent and blind assessors at each centre will assess implant stability. Bone level changes and aesthetic evaluation will be done by a single blinded and independent assessor who will evaluate the outcomes of all centers.

The principles outlined in the Declaration of Helsinki on clinical research involving human subjects will be adhered to. A written informed consent will be obtained for each patient.

The trial will be reported according to the CONSORT statement for improving the quality of reports of parallel-group randomized trials (http://www.consort-statement.org/).

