# Inclusion criteria

Any patient requiring at least one single immediate post-extractive implant in the posterior jaw (molar areas only), being at least 18 year old and able to sign an informed consent. There must be sufficient bone to allow the placement of an implant at least a 7 mm-wide and 7 mm-long.

Preoperative radiographs have to be taken. Investigators are free to choose the most appropriate examination according to the clinical case (intra-oral, panoramic, CT scans, etc.).

Patients will be grouped into: 1) non smokers; 2) moderate smokers (up to 10 cigarettes/day); 3) heavy smokers (more than 10 cigarettes/day), according to what they declare.

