### Study population and number of patients to be included

Prior to enrollment, all patients will be asked to read and if they understood it, to sign an informed consent form to document that they understand the scope of the study (including procedures, follow-up evaluations, and any potential risks involved), were allowed to ask questions pertaining to this study, and were apprised of treatment alternatives. The study is open to qualifying patients without regard to sex or race. Seventy patients will be included, 35 in each group, each center treating 10 patients each.

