### **OPERATIVE PROCEDURES**

Please complete APPENDIX 2 (Surgical and prosthetic CRF)

**Prophylactic therapy**: Patients will be administered 1 g amoxicillin 3 times a day for 6 days starting the day before tooth extraction. Patients allergic to penicillin will be prescribed clindamycin 300 mg 3 times a day for 6 days starting the day before the intervention.

Patients will rinse with chlorhexidine mouthwash 0.2% for 1 minute prior to the intervention.

Local anaesthesia: Articain with adrenaline 1:100.000.

**Tooth extraction**: Tooth extractions should be performed as atraumatically as possible attempting to preserve the buccal alveolar bone. Extraction sockets have to be carefully cleaned from any remains of granulation tissue. The wider diameter of the socket will be measured with a periodontal probe and reported in mm.

**Disclosure of the randomised allocation**: Once the tooth has been extracted and whether there is sufficient buccal bone, the patient will be finally included in the study and the operator will know whether the patient will receive large or conventional diameter implant by opening a sealed envelope. It is absolutely forbidden to open the envelope containing the randomisation code before. It will be reported in the Surgical and prosthetic CRF (APPENDIX 2) the patient sequential number contained in the envelope and to which group the patient was allocated.

**Implant installation technique**: drills will be used to prepare the implant site as suggested by the manufacturer. The intention is to stabilize the implant in the post-extractive site. Implants will be placed slightly subcrestally, about 1 to 2 mm below the most apical bone peak. The largest residual gap between the bony walls and the implant will be measured with a periodontal probe in mm. Any residual gap between the implant and the socket walls will be filled with granular bone substitute. No other grafting material is allowed.

Healing abutments will be placed and occlusal pictures showing the implants in place will be taken.

A periapical radiograph just after implant placement has to be taken.

Implants will be left to heal non-submerged for 4 months.

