### Statistical analysis

All data analysis will be carried out according to a pre-established analysis plan by a biostatistician with expertise in dentistry blinded to group allocation. A comparison of the baseline characteristics between groups will be presented. Differences in the proportion of crown/implant failures and other complications will be compared

between the groups using a chi-square test. Means of continuous variables (marginal bone level changes, aesthetic scores) will be compared using an independent sample t-test. Comparisons between, 1 and 5 years with the baseline measurements will be made by paired tests to detect any changes in marginal bone level changes for each study group with the baseline value as a covariate. All statistical comparisons will be conducted at the 0.05 level of significance.

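### The between-arm t-test leaves unused two plausible prognostic variables that are already collected; a prespecified adjusted comparison is a cheap improvement, not the repair of an error

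*Protocol*

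**What the plan says.** The Statistical analysis section names the test for the continuous outcomes: "Means of continuous variables (marginal bone level changes, aesthetic scores) will be compared using an independent sample t-test". The only covariate in that section belongs to the within-group comparisons over time, which are made "for each study group with the baseline value as a covariate". The comparison between arms has none. Baseline characteristics are to be compared and presented, but nothing is said about acting on what that comparison shows. The section also refers to an analysis plan established in advance, which is not at hand.

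Two variables are collected early enough to serve as covariates:

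- **Smoking.** Under Inclusion criteria: "Patients will be grouped into: 1) non smokers; 2) moderate smokers (up to 10 cigarettes/day); 3) heavy smokers (more than 10 cigarettes/day").
- **Socket diameter.** Under Operative procedures, in the tooth extraction step: "The wider diameter of the socket will be measured with a periodontal probe and reported in mm". The step that discloses the allocation comes after it. Study Design agrees on the order: "operators will know about the intervention to be delivered by opening a sealed envelope after the tooth has been extracted".

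Study Design describes computer-generated numbers in sealed envelopes and mentions no stratification by either variable. On size, the protocol says: "Seventy patients will be included, 35 in each group, each center treating 10 patients each".

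**The concern.** The trial compares 7.0 mm with 5.0 mm implants placed in fresh sockets. Socket width and implant width together largely determine the gap that is left to be filled and to heal. Socket diameter is therefore the patient feature closest to the randomised factor. Smoking is considered important enough to be recorded in three grades. If either variable predicts bone level change or aesthetic score, an unadjusted comparison leaves the variance it explains in the error term. A chance difference between the arms then also carries into the estimate of that particular trial. With 35 per arm, moderate chance differences are common.

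Timing matters as well. The baseline comparison will be seen. If it shows an imbalance in socket width or smoking, an adjustment added at that point would be driven by the data, while leaving it out would leave the estimate open to challenge. Naming the covariates beforehand avoids both.

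**Working it through.** **Inputs from the protocol.** n = 35 per arm and 70 in total (Study population). Significance level: "All statistical comparisons will be conducted at the 0.05 level of significance". The test is taken as two-sided because the null hypothesis in Aims is that "there is no difference in clinical outcomes between the two procedures, against the alternative hypothesis of a difference". The protocol gives no effect size, SD or power, so its sample size cannot be reproduced. Results are in units of the outcome SD.

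**Assumed input.** R², the share of outcome variance that socket diameter and smoking group explain together. The protocol gives no value, so a range from 0 to 0.30 is shown.

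**Unadjusted t-test.** The standard error is √(2/35) = 0.239 SD. With the noncentral t on 68 df, power at a difference of 0.5 SD is 54%, and 80% power needs a difference of 0.68 SD.

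**Adjusted comparison.** Socket diameter takes 1 df and the three smoking groups take 2, so 3 in all, leaving 65 residual df. Relative to the t-test, the variance is multiplied by

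(1 − R²) × (1 + 3/64)

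where 64 = 2 × 35 − 6. The second factor is the average price of estimating three covariate effects. Break-even is where the product equals 1: R² = 1 − 1/(1 + 3/64) = 3/67 = 0.045.

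| R² (assumed) | Variance ratio | SE ratio | Equivalent n per arm | Power at 0.5 SD | Difference for 80% power |
|---|---|---|---|---|---|
| t-test | 1 | 1 | 35 | 54% | 0.68 SD |
| 0 | 1.047 | 1.023 | 33.4 | 52% | 0.70 SD |
| 0.05 | 0.995 | 0.997 | 35.2 | 54% | 0.68 SD |
| 0.10 | 0.942 | 0.971 | 37.1 | 56% | 0.66 SD |
| 0.20 | 0.838 | 0.915 | 41.8 | 61% | 0.62 SD |
| 0.30 | 0.733 | 0.856 | 47.8 | 67% | 0.58 SD |

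Equivalent n is 35 divided by the variance ratio. At R² = 0.20, for example, 35/0.838 = 41.8, about 19% more patients.

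**Chance imbalance.** The standardised difference between arms in a continuous baseline variable has SD √(2/35) = 0.239. An imbalance of at least 0.3 SD in socket diameter therefore has probability P(|Z| ≥ 0.3/0.239) = 0.21. If socket diameter alone explains a share R² of the outcome variance, an imbalance of 0.3 SD shifts the unadjusted estimate by 0.3 × √R²:

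- R² = 0.05: 0.07 SD
- R² = 0.10: 0.09 SD
- R² = 0.20: 0.13 SD

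The last figure is about 20% of the 0.68 SD that the trial detects with 80% power (0.134/0.68), and a little over half of one standard error (0.134/0.239 = 0.56).

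**Validity of the named test.** In a simulation of 10,000 null trials for each of R² = 0, 0.10 and 0.30, the t-test rejected in 4.7%, 4.9% and 4.7% of trials. The adjusted model rejected in 4.9%, 5.2% and 5.0%. Both hold the 5% level.

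**The case against.** The strongest objection is that nothing here is wrong. An independent-sample t-test is a valid comparison of two randomised arms, and chance imbalance is already allowed for in its standard error. That stands. A reader might infer that the t-test is biased, or that its result would be invalid if the arms differed in socket width. The protocol and the calculation do not support this: the shift shown above is conditional on a particular imbalance and averages to zero over randomisations.

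A reader might also infer that the trial certainly gives up precision. That does not follow either. The protocol does not say how strongly socket width or smoking predicts either outcome. Below an R² of about 0.045 the adjusted model is slightly worse, and at 0.05 the gain is negligible. The 0.13 SD shift combines two assumptions, an imbalance of 0.3 SD and an R² of 0.20 for socket width alone.

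Third, the separate analysis plan is not shown and may contain an adjusted analysis. This limits the point but does not remove it. The protocol does not merely leave the method open; it names the test, so a plan that adjusts would sit beside or replace a stated choice.

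Two smaller points also stand. The order of steps implies that the socket is measured before the envelope is opened, but no sentence requires it to be recorded then. And centre is a further candidate covariate (70/10 implies seven centres); that is a separate question, which this point does not settle.

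**Conclusion.** The point holds as a low-cost improvement to a stated method, not as an error. The protocol names an unadjusted between-arm test although two plausible prognostic variables are already collected, one at inclusion and one, by step order, before allocation is disclosed. Across the assumed R² of 0 to 0.30, the possible loss is about 2% of the standard error and the possible gain about 14%. This rests on R², which the protocol does not give, on a linear covariate effect, on a two-sided 5% test, and on complete data for 35 patients per arm. The case for prespecifying the covariates rests on this lopsided trade-off and on avoiding a data-driven adjustment later.

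**What to change.** - **Statistical analysis section.** For bone level change and aesthetic score, replace the t-test with a linear model on arm, socket diameter (continuous, in mm) and smoking group. Fix it before unblinding, carry it into the analysis plan, and report the unadjusted difference as a sensitivity result.
- **Operative procedures.** State that socket diameter is recorded before the envelope is opened.
- **Covariates to exclude.** State that the residual gap around the implant is not a covariate. It is measured after the allocated implant is in place and so is itself affected by allocation.
- **Optional.** An arm-by-socket-diameter term could be listed as exploratory only. It would have low power with 70 patients and uses a further degree of freedom.

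The cost is a few sentences and no new data. The statistical price is 3 degrees of freedom, and up to about 2% of the standard error if neither variable turns out to be prognostic.

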#### Outcome measures

**Crown failure:** whether it will not be possible to place the crown because of implant failure or secondary to implant failure, or crown that has to be remade for any reason.

**Implant failure**: Implant failure is defined as implant mobility and/or any infection dictating implant removal, and or/any mechanical problems rendering the implant unusable. The stability of each individual implant will be measured by the independent and blinded outcome assessor manually with a reverse torque of 20 Ncm at abutment connection and at delivery of the definitive crown, or by assessing the

stability of the crown, using the handles of two metallic instruments, at 1 and 5 years after loading.

**Biological and biomechanical complications**: will be recorded and reported by study group. Examples of biological complications are: fistula, peri-implantitis. Examples of biomechanical complications are fracture of the metal screws, loosening of the crown, fracture of ceramic.

**Peri-implant marginal bone level changes**: digital intraoral periapical radiographs will be made with the paralleling technique at implant placement, implant loading, 1 and 5 years after loading. In case of unreadable radiograph, the radiograph has to be made again. Radiographs will be converted to TIFF format with a 600 dpi resolution, and stored in a personal computer. Peri-implant marginal bone levels will be measured using the Scion Image (Scion Corporation, Frederick, MD, USA) software. The software will be calibrated for every single image using the known implant length or the diameter of the implant collar. Measurements of the mesial and distal bone crest level adjacent to each implant will be made to the nearest 0.01 mm. Reference points for the linear measurements will be: the coronal margin of the implant collar and the most coronal point of bone-to-implant contact. Bone levels will be measured at both mesial and distal sides and averaged. Bone level at single implants will be averaged at group level.

Aesthetic evaluation of the clinical pictures, taken at delivery of the final restorations, 1 and 5 years follow-ups, on a computer screen by an independent blinded dentist. The pictures of the vestibular and occlusal aspects have to include the 2 adjacent teeth, when present. The aesthetic evaluation will be done following the pink aesthetic score(1).

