# Drop-outs

All drop-outs should be reported and the reason for dropping out should be investigated and reported per study group in APPENDIX 4. None of the included patient can be excluded for any reasons by the clinical investigators.

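### The t-test named for bone level change and aesthetic score leaves patients lost between years 1 and 5 out of the 5-year comparison, although their earlier readings could inform it

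*Protocol*

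**What the plan says.** The protocol's Statistical analysis section names one between-arm method for the continuous outcomes: "Means of continuous variables (marginal bone level changes, aesthetic scores) will be compared using an independent sample t-test". Within each arm it adds: "Comparisons between, 1 and 5 years with the baseline measurements will be made by paired tests". Those paired tests also need the later reading, so they recover nothing for a patient who is absent at 5 years.

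Under Outcome measures, "digital intraoral periapical radiographs will be made with the paralleling technique at implant placement, implant loading, 1 and 5 years after loading". Aesthetic photographs are taken at crown delivery, 1 year and 5 years. The Publication plan lists a 1-year and a 5-year report.

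On losses, the Drop-outs section says: "All drop-outs should be reported and the reason for dropping out should be investigated and reported per study group in APPENDIX 4". It gives no expected rate and does not say how a partly followed patient enters the analysis. The size is stated without power, SD or drop-out allowance: "Seventy patients will be included, 35 in each group". Statistical analysis also refers to a pre-established analysis plan, which is not among the documents.

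**The concern.** A two-sample t-test at 5 years takes one 5-year value per patient. A patient who leaves in year 3 with a sound implant has no such value, so the 5-year comparison proceeds as if the patient had never been observed, although readings up to 1 year are on file.

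Two things are at stake. The first is precision, in a trial with 35 patients per arm and no scheduled study reading between years 1 and 5. The second is bias. If those who leave are not typical of their arm at 1 year, and this plays out differently in the two arms, the difference among patients who stay is not the difference in the groups as randomised. The 1-year readings carry information about this that the named test cannot use.

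The point concerns patients lost with the implant in place. Implants that were removed are a different problem.

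**Working it through.** **Inputs from the protocol.** 35 per arm (Study population); significance level 0.05 (Statistical analysis: "All statistical comparisons will be conducted at the 0.05 level of significance"), taken as two-sided because the Aims test "there is no difference in clinical outcomes between the two procedures, against the alternative hypothesis of a difference". There is no power calculation to reproduce.

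**Assumed inputs (not in the protocol).** Drop-out *d* between years 1 and 5 of 15-25%; correlation *r* between a patient's 1-year and 5-year values of 0.6-0.8; outcome SD of 1, so results are in SD units.

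**1. Detectable difference at 80% power.** Formula: (1.960 + 0.842) × √(2/n).

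- n = 35: 2.802 × √(2/35) = 0.67 SD.
- *d* = 15%, n = 29.75: 0.73 SD.
- *d* = 25%, n = 26.25: 0.77 SD.

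Most of this loss comes from the missing 5-year readings and no analysis restores it. Step 2 isolates the part that earlier readings can recover.

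**2. Recoverable precision, random drop-out.** The complete-case standard error is √(2/[35(1 − d)]). Using the 1-year value multiplies it by about √(1 − r²d).

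| d | r | Complete-case SE | Factor | SE using 1-year value | Reduction |
|---|---|---|---|---|---|
| 15% | 0.6 | 0.259 | √(1 − 0.054) = 0.973 | 0.252 | 3% |
| 15% | 0.8 | 0.259 | √(1 − 0.096) = 0.951 | 0.247 | 5% |
| 25% | 0.6 | 0.276 | √(1 − 0.090) = 0.954 | 0.263 | 5% |
| 25% | 0.8 | 0.276 | √(1 − 0.160) = 0.917 | 0.253 | 8% |

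Simulation with 35 per arm agrees: 0.273 against 0.252 SD in the last row. A wider grid (drop-out 10-30%, correlation 0.5-0.85) put the complete-case standard error 2-14% above the all-readings one.

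**3. Bias when drop-out depends on the 1-year value.** Simulation on the wider grid; the log-odds of leaving change by 1 per SD of the 1-year value, and every loss occurs after the 1-year visit.

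| Mechanism | True arm difference | Bias of complete-case 5-year difference |
|---|---|---|
| Same in both arms | none | 0 within simulation error |
| Same in both arms | 0.5 SD | −0.02 to −0.06 SD (3-12% attenuation) |
| One arm only | none | −0.05 to −0.23 SD |
| Opposite in the two arms | none | −0.09 to −0.43 SD |

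The all-readings estimate had bias of at most about 0.005 SD throughout.

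**4. Hand check of the one-arm row.** The bias should be about *r* times the shift in the 1-year mean among those who stay. With 20% drop-out and the slope above, numerical integration gives a shift of −0.173 SD. At *r* = 0.7 the bias is then 0.7 × (−0.173) = −0.12 SD. The simulation gave −0.128 SD, with about 22% leaving in that arm.

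**The case against.** **It may be settled in the analysis plan.** That plan is not shown, and the handling of missing visits commonly belongs there. The protocol does not say that the t-test is restricted to observed cases, and a t-test after multiple imputation would use the earlier readings. This stands as a limit: a missing imputation rule is no fault of the protocol. The point rests on the test that the protocol does name. Its plain reading is one value per patient at each visit, and a mixed model in the plan would depart from it.

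**Three stronger readings are tempting, and the protocol does not support them.**

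- A reader might infer that all readings of drop-outs are thrown away. They are not: the 1-year readings of patients who leave later enter the 1-year comparison and the 1-year report. Patients lost before year 1 have no 1-year reading to lose.
- A reader might infer that the loading film enters no between-arm comparison. The t-test is applied to bone level changes without limiting the visits, and baseline is not defined, so the loading film may well be used.
- A reader might infer that drop-out linked to the 1-year result is enough to bias the difference. It is not: with a common mechanism and no arm difference the bias is zero.

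**The effect is modest and rests on assumptions.** The Exclusion criteria rule out patients who cannot commit to 5 years, and all patients are recalled every 6 months; both should limit losses. Nothing in the protocol points to drop-out that differs by arm, although operators know the allocation once the envelope is opened. A bias of 0.15 SD is about half of one standard error (0.15/0.273 = 0.55). All of this stands. The t-test is a valid test, and the case for change is that a better use of data already collected costs almost nothing.

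**Conclusion.** The concern holds for the 5-year comparison of bone level change and aesthetic score, and only for patients lost between years 1 and 5 with the implant in place. As worded, that comparison leaves them out.

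The recoverable precision is small: about 3-8% of the standard error under the assumed drop-out and correlation. Bias is conditional. It needs drop-out that depends on the 1-year result together with arms that differ in that result or in drop-out mechanism. Under the simulated mechanism it is then roughly 0.05-0.2 SD if only one arm is affected, and 3-12% attenuation of a true 0.5 SD difference under a common mechanism. A one-arm bias of 0.15 SD would be about 22% of the 0.67 SD detectable with no drop-out (0.15/0.67).

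A reader might also infer that the 1-year readings would cure any drop-out bias. That goes too far. The near-zero bias of the all-readings estimate follows from simulating drop-out that depends only on the observed 1-year value. A patient who leaves because of deterioration after year 1 is outside that assumption.

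This is a worthwhile improvement to a stated method, not an error that invalidates the analysis.

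**What to change.** In Statistical analysis, make the between-arm analysis of each continuous outcome a linear mixed model:

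- **Terms:** arm, visit and arm-by-visit, with unstructured covariance. Visits are loading, 1 and 5 years for bone level, and delivery, 1 and 5 years for aesthetics.
- **Covariate:** the placement bone level, for the bone outcome.
- **Report:** the arm difference at 1 and at 5 years, with the t-test on observed cases kept as a sensitivity analysis.
- **Assumptions to state:** data are missing at random given the observed readings, and values after implant removal are not treated as ordinary missing data, so the model is not used to extrapolate bone levels or scores for removed implants.

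If the analysis plan already deals with missing visits, align the protocol section with it.

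The cost is wording in the protocol and the plan, with no new visits or data. The downside is a slightly more complex model that does not remove bias from drop-out driven by unobserved change after year 1.
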